#### **4.3 Concomitant Medications, Treatments, and Procedures**

During their participation on this study, subjects may continue to use concomitant medications, treatments and procedures previously prescribed to treat non-cancer related conditions provided that, in the Investigator's judgment, they will not interfere with the study outcomes.

Use of proton pump inhibitors are prohibited during the study.

Although SPH4336 is mainly metabolized by CYP3A4, the impact of CYP3A4 inhibitors or inducers on SPH4336 PK has not been characterized in humans. Consequently, drugs, herbal medicines and substances that strongly inhibit or induce CYP3A4 will be prohibited during the study. Moderate inhibitors or inducers of CYP3A4 are to be used with caution. Examples of strong and moderate inhibitors and inducers of CYP3A4 include, but are not limited to:

- Strong inhibitors - boceprevir, cobicistat, danoprevir, ritonavir, elvitegravir, grapefruit juice, itraconazole, ketoconazole, lopinavir, paritaprevir and (ombitasvir and/or dasabuvir), posaconazole, saquinavir, tipranavir, telithromycin, troleandomycin, voriconazole;
- Moderate inhibitors - aprepitant, ciprofloxacin, conivaptan, crizotinib, cyclosporine, diltiazem, dronedarone, erythromycin, fluconazole, fluvoxamine, imatinib, tofisopam, verapamil;
- Strong inducers - apalutamide, carbamazepine, enzalutamide, mitotane, phenytoin, rifampin, St. John's wort; and,
- Moderate inducers - bosentan, efavirenz, etravirine, phenobarbital, primidone.

#### **4.4 Prophylactic Medications, Treatments, and Procedures**

The use of prophylactic medications intended to reduce toxicity associated with SPH4336 will not be allowed initially.

The SRC may elect to institute the use of prophylactic medications (e.g., for prevention of nausea and vomiting secondary to study medication) during the study. The specific medications used will be in keeping with generally accepted standards of care and the institutional guidelines of the participating sites.

#### **4.5 Rescue Medications, Treatments, and Procedures**

The Investigator will determine the appropriateness and use of any medications, treatments or procedures required to treat study-related toxicities or complications (e.g., treatment of drug-induced nausea or vomiting, treatment of drug-induced myelosuppression or anemia). Any rescue medication, treatments or procedures will be consistent with accepted medical practice and institutional guidelines.

#### **4.6 Prohibited Cancer Treatments**

Other medications/therapies intended to treat the subjects' underlying cancer are prohibited during the study (investigational or approved).

#### **4.7 Discontinuation of SPH4336 Administration**

SPH4336 may no longer be administered to a subject in the event of any of the following:

- Clinically and/or radiologically significant progressive disease;

- Unacceptable adverse event(s) considered secondary to SPH4336 despite appropriate therapy;
- Withdrawal of consent for SPH4336 administration by the subject (subject may agree to continued follow-up for safety and long-term outcome endpoints);
- Noncompliance by the subject as determined by the Investigator with agreement from the Medical Monitor; or,
- Termination of study by the Sponsor.

#### **4.8 Replacement of Subjects**

Non-evaluable subjects who are unable to complete at least two tumor assessments to evaluate efficacy (PFS at 12 weeks) may be replaced to ensure the appropriate number of subjects are fully evaluable for efficacy.

#### **4.9 Removal of Subjects from Study Follow-up**

No additional follow-up of a subject will occur in the event of any of the following:

- Withdrawal of consent for follow-up by the subject;
- Subject is lost to follow-up; or,
- Termination of study by Sponsor.

### **5 STUDY ASSESSMENTS AND EVALUATIONS**

#### **5.1 Informed Consent**

Written informed consent will be obtained prior to the performance of any study-related procedures.

#### **5.2 Screen Failures**

Subjects who have provided informed consent, but were subsequently found to be ineligible for study participation will be considered screen failures.

#### **5.3 Pharmacokinetic Assessments**

Single dose pharmacokinetic samples will be collected during Cycle 1 at the following timepoints:

- Day 1: pre-dose and 1 h, 2 h, 4 h, 6 h post-dose
- Day 2: 24 h post-dose

Multiple dose pharmacokinetic samples will be collected during Cycle 1 at the following timepoints:

- Day 15: pre-dose and 1 h, 2 h, 4 h, 6 h post-dose

- Day 16: 24 h post-dose

In addition, a single trough PK sample will be collected on the following days:

- Cycle 2 Day 1

The window for collection of PK samples will be  $\pm 25\%$  of the scheduled time.

PK analysis will be conducted as outlined in Section 10.9.

#### 5.4 Tumor Tissue Assessments

Archived tumor tissue or tissue obtained from a tumor biopsy at baseline will be examined histologically to confirm a diagnosis of a dedifferentiated or well-differentiated/dedifferentiated liposarcoma. CDK4 positivity (at least 1+ per IHC or evidence of amplification on FISH) will also be confirmed in baseline tumor tissue, if not already known. Baseline tumor biomarker (phospho-Rb, Ki-67) determinations will be performed in the first 10 study subjects. A fresh biopsy will be collected on Cycle 1 Day 15 in the first 10 subjects to determine treatment-related changes in those tumor biomarkers. Collection and processing of tumor tissue will be detailed in a laboratory manual. Briefly, tumor cores are obtained by needle (e.g., 2 mm) biopsy (5 cores or as specified by institutional policy). Tissue is fixed in formalin and embedded in paraffin for preparation of 4  $\mu\text{m}$  thickness unstained slides. Slides will be distributed to the appropriate laboratories for analysis using validated assays.

#### 5.5 PFS and Response Evaluations

Tumor assessments according to RECIST v1.1 will be performed at baseline and every 6 weeks (from C1D1) for 36 weeks, then every 12 weeks thereafter.

### 6 INVESTIGATIONAL PRODUCT

#### 6.1 Dosage forms

SPH4336 will be provided as film-coated tablets containing 100 or 200 mg SPH4336 free base (30 tablets per soda-lime glass bottle with a high-density polyethylene cap and a sealing gasket for a medicinal glass bottle).

Excipients in the formulation include the following:

- povidone K30
- cellactose® 80
- croscarmellose sodium
- magnesium stearate
- a film coating premix (gastric soluble, Opadry®, model 85G630034-CN, orange)

## **6.2 Storage**

SPH4336 tablets are stored in a secure location at ambient temperatures 20-25 °C (68-77 °F) with excursions permitted between 15-30°C (59-86°F).

## **6.3 Administration**

SPH4336 tablets should be swallowed whole, without chewing or crushing the tablets. SPH4336 will be administered at least 1 hour before eating or 2 hours after eating. SPH4336 should be taken at a consistent time each day.

On scheduled PK collection days, patients will be instructed to only take SPH4336 when instructed in the clinic.

### ***6.3.1 Missed doses***

If a patient misses a dose of SPH4336, the patient should take the dose as soon as possible, but not less than 8 hours before the next dose is due. If the next dose is due in less than 8 hours, the patient should skip the missed dose and take the next scheduled dose.

### ***6.3.2 Vomiting shortly after dosing***

If a patient vomits shortly after taking SPH4336, the patient should not retake the dose, but should resume dosing with the next scheduled dose. If vomiting persists, the patient should contact the Investigator.

## **6.4 Accountability**

SPH4336 compliance will be assessed at each visit where SPH4336 is dispensed. The study pharmacist or coordinator and clinical Investigator will maintain accurate records of receipt of all study drug, including dates of receipt. Study personnel will maintain accurate records regarding when and how much study drug is dispensed to and used by each subject in the study. Reasons for departure from the expected dispensing regimen must also be recorded. At completion of the study, to satisfy regulatory requirements regarding study drug accountability, all study drug will be reconciled and retained or destroyed according to applicable state and federal regulations and International Conference on Harmonisation (ICH) guidelines.

## **6.5 Disposal**

SPH4336 tablets must not be destroyed unless prior approval has been granted by the Sponsor or its representative. Disposal will be performed using institutional guidelines.

## **6.6 Dose Holds and Modifications**

Subjects experiencing SPH4336-related toxicity may have SPH4336 held or reduced as outlined in [Table 3](#).

**Table 3: Dose Hold Secondary to SPH4336-related Toxicity**

| Toxicity (CTCAE Grading)       | Dose Hold   | Dose modification on resumption  |
|--------------------------------|---|--|
| 1 or 2                  | No dose hold required   | None   |
| 3                       | Hold dosing until toxicity has resolved to at least Grade 1 or baseline                                       | First occurrence (of same AE): No dose reduction
Second occurrence: Reduce dose by at least 100 mg
Third occurrence: Permanently discontinue |
| 4 anemia or neutropenia | Restart dosing only if recovery to $\leq$ Grade 1 occurs in $\leq$ 14 days, otherwise permanently discontinue | First occurrence (of same AE): Reduce by at least 100 mg
Second occurrence: Permanently discontinue   |
| 4 lymphopenia           | Hold dosing until toxicity has resolved to at least Grade 1 or baseline                                       | First occurrence (of same AE): Reduce by at least 100 mg
Second occurrence: Permanently discontinue   |
| 4 (non-hematologic)     | N/A, permanently discontinue  | N/A, permanently discontinue   |

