| Dose Holds/
Modifications | 
Subjects will have their dose of SPH4336 adjusted in response to SPH4336-related toxicity as follows:
 

• Grade 1 or 2

○ No dose hold required

• Grade 3

○ Hold dosing until toxicity has resolved to at least Grade 1 or baseline

○ Reduce dose for second occurrence by at least 100 mg

○ Permanently discontinue further SPH4336 administration for third occurrence

• Grade 4 anemia or neutropenia

○ Restart dosing only if recovery to <math>\leq</math> Grade 1 occurs in <math>\leq</math> 14 days, otherwise permanently discontinue

○ If resumed, reduce dose by at least 100 mg

• Grade 4 lymphopenia

○ Hold dosing until toxicity has resolved to at least Grade 1 or baseline

○ If resumed, reduce dose by at least 100 mg

• All other Grade 4

○ Permanently discontinue further SPH4336 administration

 |
| Sample size                  | 
The following assumptions were used to determine sample size: Based on historical data, PFS at 12 weeks of <math>> 60\%</math> is considered promising and a PFS of <math>< 35\%</math> is considered not promising. A sample size of 29 subjects provides at least 90% power with type I error rate of 0.1 to decide whether the PFS rate at 12 weeks is less than or equal to 0.35 or greater than or equal to 0.60. If the number of subjects who are progression-free at 12 weeks is 14 or more, the hypothesis that the PFS rate at 12 weeks is less than or equal to 35% is rejected. If the number of subjects who are progression-free at 12 weeks is less than 14, the hypothesis that the PFS rate at 12 weeks is greater than or equal to 60% is rejected. Sample size was calculated using a single-stage Phase 2 clinical trial design. A final sample size of 33 will be utilized to account for a non-evaluable rate of 15%.
   |

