## 1.2 Cyclin-Dependent Kinases 4 and 6 (CDK4/6)

[figure not shown]
Cyclin-dependent kinases (CDKs), part of the serine/threonine protein kinase family, drive cell-cycle progression, control transcriptional processes, and regulate cell proliferation. CDK4/6 blocks the transition from the G1 to S phase of the cell cycle by blocking Rb phosphorylation and E2F release. Overexpression of the CDK4 protein leads to Rb (retinoblastoma) phosphorylation and progression in the cell cycle. Based on these effects, dysregulation of CDKs is considered to play a key role in tumorigenesis. CDK4/6 genes are widely expressed among various tumors, and high or moderate expression of CDK4/6 is commonly associated with poor survival. No CDK4/6 inhibitors are FDA-approved for the treatment of liposarcoma, however, several are approved for the treatment of post-menopausal hormone receptor-positive/human epidermal growth factor receptor 2 (HER2)-negative metastatic breast cancer including palbociclib (2015), ribociclib (2017) and abemaciclib (2018).

CDK4 is considered a potential target in WDLS/DDLS based on the amplification of CDK4 in >90% of these liposarcomas. Abemaciclib, a CDK 4/6 inhibitor, has been studied in a single-arm Phase 2 study in subjects with dedifferentiated liposarcomas where it demonstrated promising progression-free survival of 12 weeks in 76% of subjects. Median PFS was 30.4 weeks, and one subject had a partial response. Grade 3-4 toxicities included anemia (37%), neutropenia (20%), thrombocytopenia (17%) and diarrhea (7%). Similar results were reported in WDLS/DDLS patients with palbociclib treated on two different intermittent dosing regimen.

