## 4 STUDY DESIGN

This is a multicenter, non-randomized, open-label Phase 2 study of SPH4336 in subjects with CDK4-positive liposarcomas.

SPH4336 will be administered orally once each day in successive 28-day cycles until demonstration of progressive disease or the development of unacceptable toxicity.

The study will incorporate a safety lead-in for the initial 10 subjects. Safety will be evaluated after 10 subjects (minimum 1 cycle completed) are accrued to allow a full assessment of safety by a Safety Review Committee (SRC). The study will be stopped if unacceptable toxicity is observed in more than 2 subjects based on SRC recommendation.

Tumor assessments according to RECIST v1.1. will be performed at baseline and every 6 weeks (from C1D1) for 36 weeks, then every 12 weeks thereafter. PK samples will be collected in all subjects. Baseline (pretreatment) tumor tissue will be collected from all subjects to confirm histologically a liposarcoma with a dedifferentiated component and CDK4 positivity, and in the

first 10 study subjects, tumor tissue biomarkers (phospho-Rb, Ki-67) will be analyzed in baseline (pretreatment) and C1D15 tumor tissue samples.

A Safety Review Committee (SRC) will oversee study safety and will meet at a frequency commensurate with accrual during the study (e.g., after 10 subjects (safety lead-in) and 20 subjects, and as needed).

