#### **4.2 Unacceptable Toxicity**

To be considered as unacceptable toxicity, an AE must meet each of the following 2 criteria:

- Occur during the first 28 days of SPH4336 administration
- Not be incontrovertibly related to underlying disease

In addition, an AE must meet at least one of the following criteria:

- Any Grade 4 AE
- Any Grade 3 non-hematologic AE
- Any AE that results in permanent treatment discontinuation

The following are excluded from the definition of unacceptable toxicity:

- Grade 4 anemia or neutropenia that resolves within 14 days and which is not expected to recur based on a treatment modification (e.g., use of erythrocyte or neutrophil growth factors)
- Grade 4 lymphopenia
- Grade 3 headache, nausea, vomiting, diarrhea, fatigue, or pain if controlled within 72 hours
- Grade 3 electrolyte abnormalities that are asymptomatic and resolve to at least Grade 2 within 72 hours

The SRC will have the option of declaring other toxicities not listed above as unacceptable, if necessary, to ensure subject safety.

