#### **6.6.2 Criteria for resumption of dosing**

If a dose hold is implemented for SPH4336-related toxicity, in addition to the criteria listed in [Table 3](#), subjects may restart study drugs only if the following conditions are met:

- No more than 21 days has passed since the last dose of SPH4336;
- The AE is not expected to recur (per the Investigator and Medical Monitor) at the same grade with resumption of SPH4336 based on an intervention such as the addition of a prophylactic treatment (e.g., prophylactic anti-emetics), or a reduction in the dose of SPH4336; and,
- Continued administration of SPH4336 is considered to be in the subject's best interest (per the Investigator).

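### Table 3 and Section 6.6.2 conflict for one narrow restart case, and SAP 4.2 labels as protocol-defined an evaluable population that differs from the protocol's

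*Protocol*

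**What the plan says.** **Dosing.** For a related Grade 3 toxicity, Protocol Table 3 holds drug until recovery and then gives "First occurrence (of same AE): No dose reduction". Reduction starts at the second occurrence and permanent discontinuation at the third. The synopsis matches: "Reduce dose for second occurrence by at least 100 mg".

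Section 6.6.2 adds to Table 3. After a toxicity hold, "subjects may restart study drugs only if the following conditions are met". One condition is that the Investigator and Medical Monitor do not expect recurrence at the same grade, "based on an intervention such as the addition of a prophylactic treatment" or a dose reduction. Section 4.4 states: "The use of prophylactic medications intended to reduce toxicity associated with SPH4336 will not be allowed initially". The SRC may introduce prophylaxis later.

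**Evaluable population.** Protocol 10.4.3 requires one dose plus either two post-baseline disease assessments or clinical progression. SAP 4.2 attributes its definition to the protocol, but requires one dose plus either (a) two post-baseline assessments including Week 12 and 12 weeks of treatment without progression, or (b) progression while on treatment. SAP Section 7 reports that formal efficacy and biomarker analyses were dropped and expects no other change.

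**The concern.** Section 6.6.2 makes restart depend on an intervention. For a first Grade 3 event, Table 3 withholds one of the two interventions that 6.6.2 names, and Section 4.4 initially withholds the other. A site with such a subject has no clear instruction on whether to restart at 400 mg, restart at a lower dose or stop.

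Early stopping then matters to the primary endpoint through the SAP, whichever dosing rule was used. A subject who comes off drug before Week 12 without progression leaves the 12-week denominator altogether. A reader who takes the SAP's attribution at face value would not know that the protocol sets no such condition.

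**Working it through.** **1. Is the dosing conflict real, and how wide is it?** No arithmetic applies. These are the cases in which Table 3 permits resumption after a hold:

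| Event | Dose on resumption | Can the dose change itself satisfy 6.6.2? |
|---|---|---|
| First Grade 3 | No reduction | No; another measure is needed |
| Second Grade 3 | Lower by 100 mg or more | Yes |
| First Grade 4 anemia or neutropenia, recovered in 14 days | Lower by 100 mg or more | Yes |
| First Grade 4 lymphopenia | Lower by 100 mg or more | Yes |

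Only the first row conflicts. The list of interventions in 6.6.2 is open, so another measure, such as withdrawing an interacting drug, satisfies both rules. Not resuming breaches neither rule. What remains is a subject with a first related Grade 3 event, recovered within the 21 days allowed, with no other preventive measure, whom the Investigator wishes to rechallenge. Restart at 400 mg fails 6.6.2. Restart at 400 − 100 = 300 mg or below departs from the Table 3 cell.

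**2. How do the two evaluable definitions differ?** Scans fall every 6 weeks from C1D1, so two on-schedule post-baseline assessments mean Weeks 6 and 12.

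| Subject | Protocol 10.4.3 | SAP 4.2 |
|---|---|---|
| Treated 12 weeks, both scans progression-free | In | In |
| Stops drug before Week 12, both scans progression-free | In | Out |
| Stops drug before Week 12, both scans done, progression found after stopping | In | Out |
| Stops drug before Week 12, fewer than two scans, no progression | Out | Out |
| Progression on treatment at the first scan, with no second scan | In only if it counts as clinical progression | In |

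The definitions are therefore not the same. The second row loses a success and the third loses a failure, so the direction of the effect cannot be stated in advance.

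**3. Does the denominator matter to the futility decision?** SAP 5.7.2 gives 2 of 10 evaluable subjects reaching 12 weeks without progression after 13 were enrolled, and a fourteenth enrolled later. Its table stops the study at ≤2 of 10, ≤4 of 13 and ≤4 of 14. Exact (Clopper-Pearson) 95% limits for x of n are the 0.025 quantile of Beta(x, n − x + 1) and the 0.975 quantile of Beta(x + 1, n − x).

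| Count | Rate | 95% CI (%) | Boundary met? |
|---|---|---|---|
| 2/10, as in the SAP | 20.0% | 2.5 to 55.6 | Yes (≤2) |
| 2/13, other 3 not progression-free | 15.4% | 1.9 to 45.4 | Yes (≤4) |
| 2/14, fourteenth also not progression-free | 14.3% | 1.8 to 42.8 | Yes (≤4) |
| 3/14, fourteenth progression-free | 21.4% | 4.7 to 50.8 | Yes (≤4) |

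The SAP does not say whether the 13 − 10 = 3 other subjects stopped early or had not yet reached Week 12. Missing the boundary at 13 would need all three to be progression-free (2 + 3 = 5, above 4). The documents do not report that for any of them.

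**The case against.** The strongest answer on dosing is that Table 3 is a default. Section 6.6 introduces it permissively: drug may be held or reduced. Section 6.6.2 itself names dose reduction as a qualifying measure. Nothing expressly forbids a reduction at first occurrence, so a sensible Medical Monitor would allow one. The Medical Monitor shares every recurrence judgement, and the SRC may adjust dose or schedule (Section 9.3), which limits drift between sites. Section 4.4 can be read as barring only up-front prophylaxis, because 6.6.2 lists prophylactic anti-emetics as a measure after an event. Section 4.5 leaves treatment of drug-induced toxicity to the Investigator. All of this stands and makes the problem small. It does not remove it, because the cell and the synopsis still state the opposite of what 6.6.2 may require.

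A reader might infer that a first Grade 3 subject is barred from further drug, and so treated more harshly than a subject with Grade 4 neutropenia who may resume at a reduced dose. That holds only if the Table 3 cell is a prohibition, and the wording of Section 6.6 does not make it one.

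A reader might also infer a second conflict. Section 4 continues treatment "until demonstration of progressive disease or the development of unacceptable toxicity", and Section 4.2 counts "Any Grade 3 non-hematologic AE" as unacceptable. The documents do not support this. Section 4.2 has a 28-day window and lists permanent discontinuation as one of its own criteria, which would be circular as an individual stopping rule. It serves the lead-in study stop. Individual stopping is covered in Sections 4.7 and 6.8.

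On the SAP, Protocol 10.1 lets the SAP prevail where the two differ, so redefining the population is permitted. Disposition with reasons, exposure and response listings are already planned for the Safety Population. What stands is that the change is attributed to the protocol and is missing from SAP Section 7.

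**Conclusion.** Both points hold, and both are modest.

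The dosing conflict is a minor wording error confined to one Table 3 cell and the matching synopsis line. The documents do not allow its frequency to be estimated. A reader might take the abemaciclib Grade 3-4 rates in Protocol 1.2 as a guide, but those belong to another drug, pool two grades, and do not measure the narrow group defined above.

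The SAP population differs from the protocol's and is mislabelled. It removes subjects who stop before Week 12 without progression, including some whom the protocol would keep. A reader might infer that this produced the futility stop. The documents do not support that: 2/10, 2/13, 2/14 and 3/14 all meet the boundary, so the futility conclusion is unchanged. This assumes that all 14 enrolled subjects were treated and that the three unexplained subjects were not progression-free at Week 12.

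**What to change.** **Dose table (for any protocol that reuses it, as accrual has ended).** Change the first-occurrence Grade 3 cell and the synopsis to: no dose reduction required if another preventive intervention applies under 6.6.2; otherwise reduce by at least 100 mg. The cost is one cell and one synopsis line.

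**SAP and study report (now).**
- State in SAP Section 7, or in the study report, that the Efficacy-Evaluable definition is a change from Protocol 10.4.3.
- Beside the Efficacy-Evaluable tabulation, give the number progression-free at 12 weeks among all treated subjects. Use Week 12 tumor assessments on or off drug where available, and count subjects without one as not progression-free. A progression-free Week 12 scan after stopping drug must not be classed as a failure.
- List the exclusion reason for each non-evaluable subject.
- Flag the fourteenth subject, because the study closed before that subject's Week 12.

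The cost is a short statement, one extra count and one listing column from data already collected. The all-treated rate may be less favourable than the evaluable one.
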